10.1.2.2 Continuous Variable

Treatment Cohort Period 1

For continuous variables, the raw values and change from previous study baseline will be summarized by treatment group (L200/I-L/I and P-L/I) based on Safety Set at each scheduled time point in the Cumulative Study Period. The presentation format is similar as the continuous efficacy variable summary in Table 10-2.

10.2 Background Characteristics

10.2.1 Subject Disposition

Treatment Cohort Period 1

Number of subjects in the following categories will be summarized and tabulated:

- 110 All Subjects Set
- 110 FAS
- 109 ROS
- Subjects enrolled in Treatment Cohort Period 1 but never dosed

The number and percentage of subjects in each of the following disposition categories in Study 110 Treatment Cohort Period 1 for the Current Study Period will be summarized with the number in 110 FAS as the denominator:

- Completed treatment in Treatment Cohort Period 1
- Prematurely discontinued the treatment and the reasons for discontinuations
 - Last completed scheduled on-treatment assessment

- Completed Study 110 Treatment Cohort Period 1
- Prematurely discontinued the study in Treatment Cohort Period 1 and the reasons for discontinuations

Subject disposition will be summarized similarly with the number of subjects in 110 Safety Set as denominator for the Current Study Period.

Disposition table will also be provided based on 110 LCI Set and 110 [REDACTED]. A separate table summarizing the following analysis population will also be provided:

- All Subjects Set
- Safety Set
- FAS
- 109 FAS
- LCI Set

- All Enrolled Subjects for Treatment Cohort Period 1

Subject enrollment by region, country and by site will be summarized in a separate table based on all subjects enrolled into Study 110 Treatment Cohort Period 1.

A listing will be provided for subjects who discontinued treatment or who discontinued Study 110 in Treatment Cohort Period 1 with reasons for discontinuation.

Observational Cohort

Number and percentage of subjects in the following categories will be summarized:

- Enrolled in Study 110 Observational Cohort (overall, by region, country and by site)
- Completed Long-term Follow-up Visits (telephone contacts)
- Prematurely discontinued the study during the Long-term Follow-up and the reasons for discontinuations

Treatment Cohort Period 2

The number and percentage of subjects in each of the following disposition categories in Study 110 Treatment Cohort Period 2 will be summarized with the number of subjects enrolled in Treatment Cohort Period 2 as the denominator.

- Enrolled in Study 110 Treatment Cohort Period 2 (overall and by site)
- Enrolled and dosed in Study 110 Treatment Cohort Period 2
- Enrolled in Study 110 Treatment Cohort Period 2 but never dosed
- Completed treatment in Treatment Cohort Period 2
- Prematurely discontinued the treatment in Treatment Cohort Period 2 and the reasons for discontinuations

- Completed Study 110 Treatment Cohort Period 2
- Prematurely discontinued the study in Treatment Cohort Period 2 and the reasons for discontinuations

A listing will be provided for subjects who discontinued treatment or who discontinued study in Treatment Cohort Period 2 with reasons for discontinuation.

10.2.2 Demographics and Baseline Characteristics

Treatment Cohort Period 1 and Observational Cohort

Demographic, baseline characteristics and medical history with respect to the previous studies will be summarized by treatment groups of the Current Study Period based on 110 FAS for Treatment Cohort Period 1, 110 Safety Set for Treatment Cohort Period 1, and based on Observational Cohort separately.

Demographics:

- Age (years)
- Age (< 9 years and \geq 9 years)
- Sex (female and male)
- Ethnicity (Hispanic or Latino, not Hispanic or Latino, and not collected per local regulations)
- Race (White, Black or African American, Asian, American Indian or Alaska Native, Native Hawaiian or Other Pacific Islander, Not collected per Local Regulation, and Other)
- Geographic region (North America, Europe, and Australia)

Characteristics of previous studies baseline (the summary below is the baseline summary unless otherwise specified):

- Weight (<25 kg and \geq 25 kg)
- Weight (kg)
- Weight z-score
- Height (cm)
- Height z-score
- BMI (kg/m²)
- BMI z-score
- Sweat Chloride
- ppFEV₁
- ppFEV₁ (<90, and \geq 90)
- FEV₁ (L)
- Forced vital capacity (FVC, L)

- ppFVC (L)
- Forced expiratory flow, midexpiratory phase (FEF_{25-75%}, L/sec)
- ppFEF_{25-75%}
- FEV₁/FVC
- Percent predicted FEV₁/FVC
- Forced expiratory time (FET, sec)

- Received dornase alfa before first dose of study drug (Yes, No)
- Received any inhaled antibiotic before first dose of study drug (Yes, No)
- Received any inhaled bronchodilator before first dose of study drug
 - Yes [Short-Acting Only, Short-Acting and Long-Acting or Long-Acting only]
 - No
- Received any inhaled hypertonic saline before first dose of study drug (Yes, No)
- Received any inhaled corticosteroids before first dose of study drug (Yes, No)
- *Pseudomonas aeruginosa* status at baseline
 - Positive
 - Non-mucoid only
 - Mucoid only
 - Non-specific only
 - Non-mucoid and Mucoid
 - Non-mucoid and Non-specific
 - Mucoid and Non-specific
 - Non-mucoid and Mucoid and Non-specific
 - Negative

For Treatment Cohort Period 1, similar demographic and baseline characteristics tables will be provided based on the previous studies baseline for 110 LCI Set and 110 [REDACTED], with the following additional LCI related baseline summaries:

- LCI_{2.5}
- LCI_{2.5} (<7.5 and ≥7.5)

- LCI5.0
- Functional Residual Capacities (FRC)

Treatment Cohort Period 2

Demographic information of subjects enrolled into Treatment Cohort Period 2 will be summarized with respect to the previous studies with the following:

- Age (years)
- Age (< 9 years and \geq 9 years)
- Sex (female and male)
- Ethnicity (Hispanic or Latino, not Hispanic or Latino, and not collected per local regulations)
- Race (White, Black or African American, Asian, American Indian or Alaska Native, Native Hawaiian or Other Pacific Islander, Not collected per Local Regulation, and Other)

The important protocol deviation programming rules (based on the clinical database) are provided in Appendix I. Important protocol violations/deviations (based on the clinical database or from the site deviation log) will be summarized descriptively based on the 110 FAS. Important protocol deviations/violations will be provided as a subject data listing, indicating the source (clinical database versus site deviation log).

10.2.3 Prior and Concomitant Medications

Treatment Cohort Period 1

Medications used in this study will be coded by using the World Health Organization Drug Dictionary which is the Global dictionary that includes Enhanced and Herbal dictionaries (WHODD). Number and percentage of subjects with prior medication and concomitant medications will be summarized for the Previous Study Period based on the Safety Set, the Current Study Period based on 110 Safety Set, and the Cumulative Study Period based on the Safety Set, for the following:

- **Prior medication:** medication continued or newly received before the first dose of study drug in the previous study. The prior medication will be the same for Current Study Period and Cumulative Study Period.

Previous Study Period

- **Concomitant medication:** medication continued or newly received during the treatment-emergent period of the Previous Study Period.
- **Post-treatment medication:** any medication continued or newly received after the end of treatment-emergent period of the Previous Study Period. This is only defined for those subjects not dosed in Study 110.

Current Study Period

- **Concomitant medication:** medication continued or newly received during the treatment-emergent period of the Current Study Period.

- **Post-treatment medication:** any medication continued or newly received after the end of treatment-emergent period of the Current Study Period.

Cumulative Study Period

- **Concomitant medication:** medication continued or newly received during the treatment-emergent period of the Cumulative Study Period.
- **Post-treatment medication:** any medication continued or newly received after the end of treatment-emergent period of the Cumulative Study Period.

A given medication can be classified as a prior medication, a concomitant medication, or a post-treatment medication; both prior and concomitant; both concomitant and post-treatment; or prior, concomitant, and post-treatment. If a medication has a missing or partially missing start/end date or time and it cannot be determined whether it was taken before initial dosing, concomitantly, or more than 28 days after the last dose of study drug, it will be considered as prior, concomitant, and post-treatment.

Prior medications and concomitant medications will be summarized descriptively by preferred names. Concomitant medications with a frequency of $\geq 5\%$ at the preferred name level in any treatment group will be summarized descriptively by preferred names. Post-treatment medications will be listed for each subject.

Details for imputing missing or partial start and/or stop dates of medication are described in Appendix E.

In addition, to evaluate whether the medications have stable use after receiving study drug, shifts from use prior to the first dose (Yes, No) in previous studies to use during the treatment-emergent period (chronic versus intermittent, intermittent will be further categorized as “no use” versus “Intermittent (Excluding No Use)”) will be summarized using number of subjects and percentages for the three Study Periods following Table 10-3 for the following medication categories:

- Inhaled antibiotics
- Inhaled bronchodilator
- Inhaled hypertonic saline
- Inhaled corticosteroids
- Dornase alfa

A medication is considered to be used chronically during the treatment-emergent period if it is used on $\geq 25\%$ days during the treatment-emergent period; and is considered to be used intermittently (including no use) during the treatment-emergent period if it is used on $<25\%$ days during the treatment-emergent period.

10.2.4 Study Drug Exposure

Treatment Cohort Period 1

Study drug exposure will be summarized for the Previous Study Period based on Safety Set, for the Current Study Period based on 110 Safety Set, and for the Cumulative Study Period based on Safety Set.

Duration of exposure is defined as: last available dose date of the Study Period – first dose date of the same Study Period + 1 day, regardless of 1) unplanned interruptions, 2) the Roll-Over Gap between Previous Study and Study 110 and 3) the 2-week planned wash-out period for subjects from Study 011B for the summary of study drug exposure for the Cumulative Study Period. Duration/cumulative duration of study drug exposure will be summarized descriptively as a quantitative variable (number, mean, SD, SE, median, min, and max) for:

- Previous Study Period (Studies 109/011B) based on Safety Set with two treatment groups (L200/I, Placebo);
- Current Study Period (Study 110) based on 110 Safety Set with two treatment groups (L200/I-L/I, P-L/I) and Overall;
- Cumulative Study Period based on Safety Set with L200/I-L/I, and Current Study Period based on 110 Safety Set with P-L/I, pooled together. The pooled treatment group is presented as L/I Overall.

Additionally, the total duration of study drug exposure, defined as the sum of the subject's duration of treatment exposure and expressed in patient years, will be provided.

Duration/cumulative duration of exposure will also be summarized as a categorical variable: ≥ 1 dose of study drug to <24 weeks, ≥ 24 to <48 weeks, ≥ 48 to <72 weeks, ≥ 72 to <96 weeks, ≥ 96 weeks to 120 weeks, and ≥ 120 weeks.

10.2.5 Study Drug Compliance

Treatment Cohort Period 1

Study drug compliance for each Study Period (the Previous Study Period, Current Study Period and Cumulative Study Period) in Treatment Cohort Period 1 will be calculated as follows respectively:

$$100 \times [1 - (\text{Total number of days study drug interrupted in a Study Period in Treatment Cohort Period 1}) / (\text{Duration of study drug exposure in the Study Period in Treatment Cohort Period 1} + \text{Total number of days study drug interrupted after last dose in the Study Period in Treatment Cohort Period 1, if any})].$$

Note: A subject may have treatment interruption first, followed by permanent treatment discontinuation. In such cases, drug interruption would be after the last dose date of the corresponding Study Period.

The total number of days of study drug interrupted in a Study Period is defined as the sum of (number of days of study drug interrupted in each interval in the Study Period), where number of days of study drug interrupted in each interval in the Study Period is defined as the interruption end date - the corresponding interruption start date + 1.

Percent of tablets taken in Treatment Cohort Period 1 will be calculated as follows:

$$100 \times (\text{Total number of tablets administered in a Study Period in Treatment Cohort Period 1}) / [4 \times (\text{Duration of study drug exposure in days in the Study Period in Treatment Cohort Period 1})]$$

1+ Total number of days study drug interrupted after last dose in the Study Period in Treatment Cohort Period 1, if any)].

Subjects having calculated percent of tablets taken >100% will be considered as 100% in percent of tablets taken.

In calculating the total number of days study drug being interrupted, only the interruptions with duration of ≥ 3 days will be considered. An interruption with duration of < 3 days will not be considered in the calculation.

Treatment compliance and percent of tablets taken will be summarized descriptively (n; mean, SD, SE, median, min, and max in days) and will be tabulated for:

- 1) Previous Study Period based on Safety Set by treatment groups (L200/I and Placebo);
- 2) Current Study Period based on 110 Safety Set by treatment groups (L200/I-L/I and P-L/I) and Overall;
- 3) Cumulative Study Period based on Safety Set with L200/I-L/I, and Current Study Period based on 110 Safety Set with P-L/I, pooled together. The pooled treatment group is presented as L/I Overall.

A list of subjects with <80% compliance in Treatment Cohort Period 1 will be provided. The number and percentage of subjects whose compliance is <80% or $\geq 80\%$ and the number and percentage of subjects whose percent of tablets taken is <80% or $\geq 80\%$ in Treatment Cohort Period 1 will be summarized.

Treatment Cohort Period 2

Study drug compliance for Treatment Cohort Period 2 will be calculated as follows:

$$100 \times [1 - (\text{Total number of days study drug interrupted in Treatment Cohort Period 2}) / (\text{Duration of study drug exposure in Treatment Cohort Period 2} + \text{Total number of days study drug interrupted after last dose in the Treatment Cohort Period 2, if any})].$$

Note: A subject may have treatment interruption first in Treatment Cohort Period 2, followed by permanent treatment discontinuation in Treatment Cohort Period 2. In such cases, drug interruption would be after the last dose date of the Treatment Cohort Period 2.

The total number of days of study drug interrupted in the Treatment Cohort Period 2 is defined as the sum of (number of days of study drug interrupted in each interval in the Treatment Cohort Period 2), where number of days of study drug interrupted in Treatment Cohort Period 2 is defined as the interruption end date - the interruption start date + 1.

In calculating the total number of days study drug being interrupted, only the interruptions with duration of ≥ 3 days will be considered. An interruption with duration of < 3 days will not be considered in the calculation.

Study drug compliance during the Treatment Cohort Period 2 will be listed.

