Subjects who were enrolled but had Day 1 study drug administration procedures (Section 10.2) delayed more than 1 calendar day will have to repeat all assessments (with the exception of the ophthalmologic examination if performed within the last 3 months before) that were specified to be performed at the Day 1 visit before receiving their first dose of study drug.

Timing of Day 1 Visit in Study 110 Nonactive Sites

The Day 1 Visit of Study 110 **will NOT coincide** with the Week 24 Visit (last Treatment Period visit) of Study 109 or the Week 26 Visit (Safety Follow-up Visit) of Study 011B for subjects at Study 110 sites that have NOT been activated by the time the Week 24 Visit (Study 109) or the Week 26 Visit (Study 011B) has been completed. Subjects at these nonactive sites will have to repeat any Study 110 Day 1 assessments (in addition to completing Study 110-specific Day 1 events/assessments) that were specified to be performed at the Week 24 Visit (Study 109) or the Week 26 Visit (Study 011B) except for the ophthalmologic examination (if the ophthalmologic examination was performed within the last 3 months before the visit). Assessments for the Treatment Cohort for are listed in

Table 3-1. Subjects will be outpatients during the Treatment Period. All visits should occur within the windows specified.

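### Cumulative Study Period: percent of tablets taken is understated because washout and roll-over gap days stay in the denominator, and the same days slightly dilute real interruptions in the companion measure

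*SAP*

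**What the plan says.** SAP 10.2.4 defines duration of exposure as "last available dose date of the Study Period – first dose date of the same Study Period + 1 day". It applies this "regardless of 1) unplanned interruptions, 2) the Roll-Over Gap between Previous Study and Study 110 and 3) the 2-week planned wash-out period", the washout clause being tied to the cumulative exposure summary.

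SAP 10.2.5 then uses that duration in two adherence measures, for each Study Period including the cumulative one:

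- Compliance is 100 × [1 − interrupted days / (duration + interrupted days after the last dose)]. Its numerator is "Total number of days study drug interrupted in a Study Period in Treatment Cohort Period 1", and only interruptions of 3 days or more count.
- The tablet measure is introduced with "Percent of tablets taken in Treatment Cohort Period 1 will be calculated as follows": 100 × tablets administered / [4 × (duration + interrupted days after the last dose)], capped at 100%.

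Neither denominator removes the washout or the gap. Both measures are split at 80%; for tablets the SAP asks for "the number and percentage of subjects whose percent of tablets taken is <80"% or at least 80%. The L/I Overall column pools L200/I-L/I subjects over the Cumulative Study Period with P-L/I subjects over the Current Study Period only.

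The SAP does not say whether washout or gap days count as interruptions. Protocol 12.4.2.4 describes the Study 011B washout as a planned interruption.

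**The concern.** A span that ignores breaks is a reasonable description of how long a child was followed from first to last dose. It is not a count of days on which tablets were due. Used as the latter, it charges a child with four missed tablets for every day of a break that the design itself imposed.

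The same days act the other way in the interruption-based measure. If they are not recorded as interruptions, they enlarge the denominator without adding to the numerator, so they count as days of perfect compliance. The two measures are then off in opposite directions for the same child.

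At stake is the description of adherence in the L/I Overall column: the means, and the split at 80%. No efficacy model or analysis set uses either measure.

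**Working it through.** The documents give no compliance result to reproduce, so the SAP formulas are applied to a child who takes 4 tablets on every dosing day.

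**Inputs**

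- Parent-study dosing: 24 weeks = 168 days (Protocol 9.1).
- Study 110 dosing: to the Week 96 target day, 673 (SAP Appendix D). A child who stops at Study 110 Week 24 has 169 days.
- Dosed days D: 168 + 673 = 841 for a completer; 168 + 169 = 337 for the Week 24 leaver. Taking 96 weeks as 672 days (D = 840) gives the same completer percentages to one decimal.
- Planned washout, Study 011B: Week 24 to Week 26 = 14 days (Protocol 9.1).
- Roll-Over Gap: no length and no maximum is stated. Total undosed periods g of 28, 56 and 91 days (4, 8 and 13 weeks) are assumptions.

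**Percent of tablets, every tablet taken** = 100 × 4D / [4(D + g)] = 100 × D / (D + g)

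| Undosed days g | Completer (D = 841) | Week 24 leaver (D = 337) |
|---|---|---|
| 14 (washout only) | 841/855 = 98.4% | 337/351 = 96.0% |
| 28 | 841/869 = 96.8% | 337/365 = 92.3% |
| 56 | 841/897 = 93.8% | 337/393 = 85.8% |
| 91 | 841/932 = 90.2% | 337/428 = 78.7% |

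**When does this child fall below 80%?** D / (D + g) < 0.80 requires g > 0.25 × D.

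- Completer: 0.25 × 841 = 210.25, so at least 211 undosed days.
- Week 24 leaver: 0.25 × 337 = 84.25, so at least 85 undosed days.
- Washout alone, worst case, with a single day dosed in Study 110: 169/183 = 92.3%. The washout can never produce a value under 80%.

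**Interruption-based compliance**

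- Same child, washout and gap not counted as interruptions: 100 × [1 − 0/(D + g)] = 100% for any g.
- Same child, washout counted as an interruption: 1 − 14/855 = 98.4%. The SAP does not settle which reading applies.
- A completer with 170 genuinely interrupted days: 1 − 170/840 = 79.8% on dosing days, against 1 − 170/854 = 80.1% with the 14-day washout left in. This child moves across the cut-off.

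**The case against.** The strongest reply is that the effect is small and the convention is disclosed. SAP 9.1.3 says that all analyses are run regardless of the gap and warns that cumulative results may differ from the separate studies combined. SAP 9.1.1 expects most children to start Study 110 on the day of the last parent-study visit. Both measures are also tabulated for the Current Study Period, where these days do not arise, and the important-deviation rule in Appendix I uses Study 110 compliance. All of this stands, and it limits the size. It does not make the figure right: ignoring breaks suits an exposure span but not a count of tablets due.

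Three stronger readings are tempting and are not supported.

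- A reader might infer that both measures make a fully adherent child look non-adherent. The interruption formula uses no tablets and, read literally, gives that child 100%.
- A reader might infer that adherent children will be put below 80%. The only value under 80% in the table combines an assumed 13-week undosed period with leaving at Study 110 Week 24.
- A reader might take the eye-examination waiver at nonactive sites, "if the ophthalmologic examination was performed within the last 3 months before the visit", as evidence of gaps longer than 3 months. It concerns the age of an examination, which may predate Week 24, and gives no gap length.

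**Conclusion.** Wrong as written; minor. In the Cumulative Study Period, percent of tablets taken is too low for children with a washout or a gap. The certain part is about 1.6 points for an adherent Study 011B completer, in up to about 56 children. Anything larger depends on gap lengths that the documents do not give. Crossing 80% on tablets is hypothetical, since undosed days must exceed a quarter of dosed days. The interruption-based measure errs slightly upward for children with real interruptions, provided that washout and gap days are not recorded as interruptions.

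The effect is confined to L200/I-L/I subjects in the L/I Overall column. Same-day Study 109 rollovers, Current Study Period figures and the important-deviation rule are unaffected. No primary safety or efficacy conclusion changes.

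**What to change.** For the Cumulative Study Period, subtract from the duration in both denominators the calendar days strictly between the last parent-study dose date and the first Study 110 dose date. The subtraction is zero if those dates are the same or consecutive, or if the child was not dosed in Study 110. Keep the term for interrupted days after the last dose. State that the washout and gap days are not counted as interruptions. A child who took every tablet then scores 100% on both measures whatever the gap.

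Subtracting is safer than adding the two dosing spans. Protocol 10.2 allows the last Study 109 dose and the first Study 110 dose on one day, at least 6 hours apart. Two spans that each add 1 would count that day twice and show an adherent completer at 841/842 = 99.9%.

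One case needs its own line. Protocol 9.1 lets children enter with sponsor approval while study drug is interrupted. Days of such an interruption that fall inside the parent treatment period are missed treatment and should stay in both the denominator and the interruption count.

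The cost is two or three sentences in SAP 10.2.5 and a small programming change. The dose dates are already needed for the exposure summaries, so no new data are required.
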